Postnatal morbidities such as respiratory distress syndrome (RDS), hemodynamic significant patent ductus arteriosus (HsPDA), grade 2-3 intraventricular hemorrhage (IVH), FI, NEC, and sepsis were noted. Gastric residual volume of more than 50% of the previous feeding volume, emesis, abdominal distention, or both, and a reduction, delay, or cessation of enteral feedings were the criteria used to define feeding intolerance (8). According to the modified Bell's criteria (9), stage II/III NEC was used as an outcome parameter. Echocardiography was used to determine the presence of HsPDA. Positive blood culture was used to define proven sepsis. The Papile classification system was used to classify IVH (10). Furthermore, the need for inotropic support during the first week of life, parenteral nutrition durations, invasive/non-invasive mechanical ventilation support, total respiratory support, oxygen support, hospitalization, and mortality were recorded.

**(b) Splanchnic near-infrared spectroscopy (NIRS) monitoring:** As soon as the infants were admitted to the NICU on the first day of life (DOL), a self-adhesive transducer (cerebral/somatic-neonatal NIRSensor) with a light-emitting diode and two remote sensors was applied to the infra-umbilical abdominal region to continuously record regional splanchnic saturation (rSO2S). Continuous rSO2S monitoring was carried out for 1 week using NIRS (INVOS 5100; Covidien Somanetics, Troy, MI), simultaneously together with continuous preductal oxygen arterial saturation (SaO2) monitoring using a pulse oximetry device (Nellcor, Covidien-Medtronic, Minneapolis, MN) with a target band of 90–95% and alarm settings of 89 and 96% in the case of oxygen therapy. Based on the simultaneous measurements of rSO2S and

$\text{SaO}_2$ , the infants' fractional tissue oxygen extractions ( $\text{FOE} = \text{SaO}_2 - \text{rSO}_2\text{S} / \text{SaO}_2$ ), which represent the balance between oxygen delivery and oxygen consumption, were assessed. After removing artifacts that may indicate sensor misplacement,  $\text{SaO}_2$  and NIRS parameters ( $\text{rSO}_2\text{S}$ ,  $\text{FOE}$ ) were calculated as means on each day of the first week of life (WOL).

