Infants with an UVC were included in the UVC (+) Study Group, while those without a catheter were included in the UVC (-) Control Group. Continuous measurements taken during the first WOL were compared both between the groups and within each group on a day-to-day basis. Splanchnic NIRS monitoring was terminated 24 hours after the removal of the UVC. In the UVC (+) Group, the day and time of catheter placement and removal were recorded. Splanchnic oxygenation measurements were compared at the following time intervals: one hour before UVC placement, one hour after UVC placement, 24 hours before UVC removal, and 24 hours after UVC removal. Additionally, the daily means in the UVC (+) Group during the period when the UVC was in place were compared with the daily means in the UVC (-) Group. Clinical parameters and splanchnic NIRS data were compared between the UVC (+) and UVC (-) Groups. The birth hemoglobin (Hb) value of the UVC (+) Group, as well as the Hb value on the day the UVC was removed, were recorded, and a repeated measures analysis was performed.

The primary outcomes included comparing continuously recorded  $\text{rSO}_2\text{S}$  and  $\text{FOE}$  values during the first WOL between the UVC (+) and UVC (-) groups, assessing  $\text{rSO}_2\text{S}$  and  $\text{FOE}$  measurements within the UVC (+) Group before and after UVC placement and removal, and determining the impact of UVC on splanchnic oxygenation. The secondary outcomes involve evaluating the relationship between UVC presence and the incidence of feeding intolerance and necrotizing enterocolitis.

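### Two unreconciled NIRS recording windows (1 week, or until 24 hours after UVC removal): whichever applied alone, one of the two primary comparisons can lose data

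*Combined protocol and SAP*

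**What the plan says.** All the recording rules are in section 2.5(b) of the combined protocol and SAP.

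- **Duration.** Starting at NICU admission on the first day of life, "monitoring was carried out for 1 week using NIRS". Daily means are then formed for each day of the first week. No group is excepted.
- **Stop.** Two paragraphs on: "Splanchnic NIRS monitoring was terminated 24 hours after the removal of the UVC". No group is named, and there is no link to the 1-week period.
- **First-week comparison.** "Continuous measurements taken during the first WOL were compared both between the groups and within each group on a day-to-day basis". First-week rSO2S and FOE between the groups is listed as a primary outcome.
- **Removal comparison.** The intervals compared include "24 hours before UVC removal, and 24 hours after UVC removal". The primary outcomes also list rSO2S and FOE "within the UVC (+) Group before and after UVC placement and removal".
- **Additional comparison.** "the daily means in the UVC (+) Group during the period when the UVC was in place were compared with the daily means" of the UVC (-) group.
- **Timing data.** "In the UVC (+) Group, the day and time of catheter placement and removal were recorded".

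Section 1.5.2 lists two-way repeated-measures ANOVA for repeated measurements, and t or Mann-Whitney tests for two groups. It does not say which serves the primary outcome, and gives no rule for missing days or unequal recording length. Section 1.2 excludes infants whose catheter came out before 24 hours. Section 1.4 gives a recommended maximum of 7-10 days. Neither gives the removal days that occurred.

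**The concern.** The two rules end recording at the same time only if the catheter comes out at about day 6. The documents allow removal well before and well after that. A UVC (-) infant has no removal time, so the second rule cannot define that group's window.

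Each rule, applied alone, puts a different primary comparison at risk. A 24-hour stop shortens the first-week record of early-removal infants in one group only. A complete-case repeated-measures ANOVA would then drop those infants, and day-by-day tests would rest on a UVC (+) subset that shrinks towards longer-catheter infants. A 1-week stop keeps the first week intact but removes part or all of the post-removal window when the catheter comes out after day 6.

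If catheter duration is unrelated to splanchnic oxygenation, the cost is precision. If it is related, the early loss can create or hide a group difference.

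**Working it through.** **Group size.** Section 1.5.1 gives 21 per group for effect size 0.8, type 1 error 0.05 and 80% power. An independent t-test needs 20.03, so 21, one-sided and 25.52, so 26, two-sided. The stated 21 therefore reproduces one-sided; sidedness is not stated. Here 21 is used only as the group size.

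**Window arithmetic.** Let d be age in days at removal, with placement assumed on day 1.

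- 24-hour stop: recording ends at d + 1, so first-week days lost = max(0, 7 − (d + 1)).
- 1-week stop: recording ends at 7, so post-removal hours kept = 24 × (7 − d), limited to 0-24.

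| Age at removal, d | First-week days lost, 24-hour stop | Post-removal hours kept, 1-week stop |
|---|---|---|
| 1 | 5 | 24 |
| 2 | 4 | 24 |
| 3 | 3 | 24 |
| 4 | 2 | 24 |
| 5 | 1 | 24 |
| 6 | 0 | 24 |
| between 6 and 7 | 0 | part |
| 7-10 | 0 | 0 |

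If recording ran to the later of the two ends, both losses are zero.

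**Infants affected under assumed removal days.** Let R be the day of life of removal. Under the 24-hour stop, day t counts as recorded if R + 1 ≥ t. With R uniform on 2-10, UVC (+) infants recorded on days 4, 5, 6 and 7 number 21 × 8/9 = 18.7, 21 × 7/9 = 16.3, 21 × 6/9 = 14.0 and 21 × 5/9 = 11.7. Under the 1-week stop, the post-removal window is full if R ≤ 6, partial if R = 7 and absent if R ≥ 8:

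| Removal days (assumed uniform) | Full | Partial | None |
|---|---|---|---|
| 2-10 | 11.7 | 2.3 | 7.0 |
| 5-10 | 7.0 | 3.5 | 10.5 |
| 6-10 | 4.2 | 4.2 | 12.6 |

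**False-positive rate of the complete-case analysis, 24-hour stop.** Assume no UVC effect, daily SD 1, within-infant correlation 0.5, and correlation ρ between an infant's underlying level and catheter duration. Complete cases are those with R ≥ 6, a share p of the group.

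- Bias = ρ × √0.5 × φ(z)/p, where z is the normal quantile at 1 − p.
- Variance of an infant's 7-day mean = 0.5 + 0.5/7 = 0.571.
- SE = √(0.571 × (1/(21p) + 1/21)).

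For days 2-10, p = 5/9, φ(z)/p = 0.711 and SE = 0.276. At ρ = 0.5, bias = 0.5 × 0.707 × 0.711 = 0.25 SD, and 0.251/0.276 = 0.91 standard errors. For days 5-10, p = 5/6, φ(z)/p = 0.300 and SE = 0.245. For days 6-10, p = 1 and nothing is lost.

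| Removal days | ρ | Bias (SD) | Rate, formula | Rate, simulation |
|---|---|---|---|---|
| 2-10 | 0 | 0.00 | 5.0% | 4-6% |
| 2-10 | 0.3 | 0.15 | 8.5% | 8-9% |
| 2-10 | 0.5 | 0.25 | 14.9% | 14-15% |
| 2-10 | 0.7 | 0.35 | 24.7% | 23-25% |
| 5-10 | 0.5 | 0.11 | 7.2% | 7% |
| 5-10 | 0.7 | 0.15 | 9.3% | 9% |
| 6-10 | 0.5 or 0.7 | 0 | 5.0% | 5% |

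Separate daily t-tests stay at 5% on days 1-3. For removal on days 2-10 they rise to about 10% (ρ = 0.5) and 15% (ρ = 0.7) on day 7.

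**The alternative analysis.** On the same simulated data (days 2-10), a mixed model with group, day, group by day and a random infant effect, averaged over the week, has bias of 0.02-0.03 SD and a false-positive rate of about 5% at ρ = 0.5 and 0.7.

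**The case against.** The best answer is that one reading satisfies every sentence: all infants were recorded for a week, and UVC (+) infants were followed further, where necessary, to 24 hours after removal. The stop appears in the same paragraph as the before/after-removal comparison, and its likely purpose was to secure that window. On this reading nothing is lost, and controls simply have the first week. This stands as a natural reading. It is not what the text says: the stop is worded as the end of monitoring, not as an extension.

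Second, the rates are conditional. The documents give neither removal days nor any link between duration and oxygenation. Early removal is allowed, but nothing shows it was common. Section 1.3 points the other way: 40 ml/kg/day rising by 15 reaches 115 on day 6 and 130 on day 7, so 120 is first passed on day 7; 10 rising by 10 reaches 120 on day 12. If catheters were kept for parenteral nutrition (an assumption), most would come out at day 6 or later, and little first-week data would be lost. This also stands, but late removal is where a 1-week stop costs most post-removal windows.

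Third, a reader might infer that the conflict is also what dilutes the UVC effect, because post-removal days count as UVC (+). The documents do not support that. It follows from comparing groups defined by ever having had a UVC over the whole first week, and it arises under any reading that keeps first-week data after removal. The additional in-place comparison already addresses it in part. That comparison, done by day, rests on fewer infants as catheters come out, whichever recording rule applied.

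**Conclusion.** The conflict is certain: section 2.5(b) gives two end points for recording and no rule between them, and both comparisons that depend on them are primary. Its consequence is not certain. It ranges from none (recording to the later end, or removals clustered near day 6) to a first-week comparison with a false-positive rate of 14% to 25%. The upper end needs four things together: the 24-hour stop, a complete-case ANOVA, removal spread over days 2-10, and a duration-oxygenation correlation of 0.5 to 0.7. At correlations of 0 and 0.3 the rate is about 5% and 8%; with removal on days 5-10 it is about 7% and 9% at 0.5 and 0.7.

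A reader might infer that first-week or post-removal data were in fact lost, or that the primary result is biased. The documents do not show either. They show that the reader cannot tell, and that the listed repeated-measures method would be fragile if days are missing. This should be fixed; confidence in its practical size is moderate.

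**What to change.** 1. Reconcile the two statements in section 2.5(b) into the one recording rule actually used, stated separately for UVC (+) and UVC (-).
2. Analyse first-week rSO2S and FOE with a linear mixed model on all available daily means, in place of a complete-case repeated-measures ANOVA: group, day of life, group by day, baseline covariates and a random infant effect. Keep the stated group comparison, for example averaged over the week.
3. An in-situ versus control contrast, coded from the recorded placement and removal times, may be reported alongside. Label it post hoc if it was chosen after data were seen.
4. Report the distribution of removal days, the number of infants contributing on each day by group, and the number with a complete 24-hour post-removal window.

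The cost is a sentence or two of wording and slightly more modelling. No new recording is needed, since the catheter times were already collected. The model cannot restore windows that were never recorded, and it does not correct for removal driven by changes that were not recorded.

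### The before/after catheter-removal contrast is a primary outcome for UVC impact, but no control comparison is aligned to removal time; early NIRS is also not named as the ANCOVA baseline

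*Combined protocol and SAP*

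**What the plan says.** Section 2.5(b) sets four comparison times in the UVC (+) group: "one hour before UVC placement, one hour after UVC placement, 24 hours before UVC removal, and 24 hours after UVC removal". Catheter placement and removal times are recorded in that group only. The primary outcomes combine the first-week comparison between groups with the UVC (+) contrast "before and after UVC placement and removal, and determining the impact of UVC on splanchnic oxygenation".

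Controls do appear elsewhere in the plan:

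- **By day of life:** "Continuous measurements taken during the first WOL were compared both between the groups and within each group on a day-to-day basis".
- **By catheter status:** UVC (+) daily means "during the period when the UVC was in place were compared with the daily means in the UVC (-) Group".
- **By model:** Section 1.5.2 lists a two-way repeated measures ANOVA with one repeated factor. For comparing time points it lists Wilcoxon (two) and Friedman (three or more).

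Section 1.5.2 also plans covariance analysis with confounding factors but names none. Monitoring began "As soon as the infants were admitted to the NICU on the first day of life", and Section 1.2 requires NIRS before placement in every UVC (+) infant.

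**The concern.** The removal contrast has no comparator on its own time axis. Between its two windows infants get older, and under Section 1.3 feeds advance where achievable. Wilcoxon and Friedman have no control term. The one comparison tied to catheter status stops when the catheter comes out. A change that controls of the same age also show could be reported as recovery from a catheter effect, within a primary outcome.

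Putting a significant UVC (+) test beside a non-significant control test would not settle the matter, because two separate tests do not test the difference between the groups.

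The baseline point is similar but smaller. The groups are formed by clinical indication and matched only on gestational age and birth weight. A difference in oxygenation that was there before placement could be carried into the first-week comparison and read as a UVC effect.

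**Working it through.** **The plan's own figure.** Section 1.5.1 gives 21 per group for an effect size of 0.8, alpha 0.05 and 80% power. A two-sample t-test calculation gives 20.03, rounded up to 21, if one-sided, and 25.5, rounded up to 26, if two-sided. The figure covers the between-group contrast; none is given for the removal contrast. Below, n = 21 per group and tests are two-sided at 0.05.

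**Assumptions.** The documents give no drift, SD or correlation. Drift is therefore expressed in SDs of each infant's before-to-after change. Data are normal and there is no catheter effect. Simulated figures use 10,000 runs, so they carry an uncertainty of up to about one percentage point.

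**1. Removal contrast.** For the one-group test, a drift of δ SD gives a paired t noncentrality of δ√21. The rejection rate reaches 10%, twice nominal, at δ = 0.149. Simulated rates were:

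| Shared drift (SD of change) | One-group Wilcoxon significant | UVC (+) significant, separate control test not | Difference in change, drift fully shared | Difference in change, controls share half |
|---|---|---|---|---|
| 0 | 4.9% | 4.7% | 5.0% | – |
| 0.25 | 18.2% | 14.8% | 4.7% | 7.0% |
| 0.5 | 55.6% | 25.3% | 4.7% | 12.2% |
| 0.75 | 88.4% | 10.3% | 4.7% | 21.9% |

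The third column agrees with p(1 − p) for independent groups: 0.182 × 0.818 = 0.149; 0.556 × 0.444 = 0.247; 0.884 × 0.116 = 0.103. The last column is a two-sample t-test with a residual drift of δ/2.

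**2. Baseline difference of 0.5 SD before placement.**

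- Unadjusted, fully persisting: noncentrality 0.5 × √(21/2) = 1.62, so 35% of trials are significant.
- Unadjusted, fading in proportion to a baseline–outcome correlation of 0.5, 0.7 or 0.9 (residual 0.25, 0.35 or 0.45 SD): 12%, 20% or 30%.
- ANCOVA on early NIRS, simulated at the same correlations: 14%, 10% or 7% if the difference persists, and about 5% if it fades.

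**3. Price of the controlled removal estimate.**

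- One-group 95% half-width: t(20)/√21 = 2.086/4.583 = 0.455 SD.
- Difference between groups: t(40) × √(2/21) = 2.021 × 0.3086 = 0.624 SD. With 16 or 12 usable UVC (+) infants against 21 controls it is 0.674 or 0.738 SD.
- Power for 0.8 SD: 72% with 21 against 21, and 65% or 57% with 16 or 12 UVC (+) infants.

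**4. Usable removals.** If control recordings end at one week, the latest removal with a complete control post-window is 7 × 24 − 24 = 144 h. Section 1.4 recommends at most 7–10 days of catheter use, Section 2.5(b) says "monitoring was carried out for 1 week using NIRS", and it also says "Splanchnic NIRS monitoring was terminated 24 hours after the removal of the UVC". On these statements, a late removal may have no control data at the same age.

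**The case against.** The first-listed primary outcome is a concurrent group comparison, and it is the only contrast the sample size covers. The natural reading of the two-way repeated measures ANOVA is group by day, and its interaction tests whether the time courses differ. That narrows the gap but does not close it: when removal ages vary, each calendar day mixes infants before and after removal.

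Section 1.5.2 does not map tests to comparisons, so using Wilcoxon or Friedman for the removal windows is an inference, though a likely one. The plan also never says it will compare separate test results, so those rates describe a possible reading of the results and not a stated method.

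If the windows are 24-hour averages, they span 48 hours but their centres are only 24 hours apart, which leaves less time for drift. All drift and imbalance sizes are assumed, and feed advancement is conditional. These points limit what can be said about size, not about the missing comparator.

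The remedy has limits too. It needs index ages for controls, loses late removals, and cannot remove the effect of recovery that prompts removal. That is why it is offered as an added analysis and not as a new primary outcome.

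**Conclusion.** The concern holds and should be fixed. A contrast confined to UVC (+) infants is a primary outcome used to judge UVC impact, and nothing in the plan aligns controls to removal time. If drift is present and shared, the one-group error exceeds 10% once drift passes about 0.15 SD of the change, and it reaches 56% at 0.5 SD. These are illustrations under assumed drift; the true size cannot be derived from the documents. The placement contrast, one hour either side, is much less exposed. The first-week comparison shows control trends by day but does not answer the removal question.

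The baseline point is smaller. It rests on an assumed pre-placement difference and on a comparable early value being obtainable in controls, who are monitored from admission. Confidence is medium overall.

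**What to change.** 1. **Removal.** Add, labelled as an added analysis, an age-aligned comparison.
   - Assign removal ages to UVC (-) infants of similar gestational age and birth weight. Section 1.2 does not state individual pairs, so describe this step.
   - Estimate the group-by-window difference in change, 24 h before against 24 h after.
   - Restrict it to removals by about 144 h and report the exclusions.
   - If control recordings were not kept, use daily means: the day before against the day after the removal day, for removals on days 2–6. This is coarser, and the UVC (+) post-removal day may be partial.
   - Keep the one-group Wilcoxon and Friedman results as descriptive, and base any statement about the effect of removal on the controlled estimate.
2. **Baseline.** In the first-week group comparison, use early NIRS as the ANCOVA baseline for rSO2S and FOE: the pre-placement value in UVC (+) infants and the same postnatal hour in controls. List any other covariates.
3. **Text.** Reconcile the catheter and monitoring periods in Sections 1.4 and 2.5(b). State that treatment started alongside the catheter, and recovery that prompts removal, remain uncontrolled.

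The cost is analysis wording, a matching step and extraction of control windows from stored recordings, which are assumed to be available. No new infants or measurements are needed. The removal estimate is less precise, as shown above, and applies only to removals within the first week.

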**1.2. Patient Enrollment and Group Formation**

The inclusion criteria were as follows: (1) parents agreed to participate in the study (2) infants born in our hospital, who were followed up in the NICU, with a gestational age of <34 weeks and a birth weight of 1000-2000 grams. Infants who indicated UVC placement, and for whom NIRS measurements were taken both before and after UVC placement were included in the UVC (+) Study Group. Infants who did not have a UVC but matched the Study Group regarding gestational age and birth weight constituted the UVC (-) Control Group.

Infants who died during the first week of life, were transferred to another hospital, had chromosomal anomalies, major congenital anomalies affecting splanchnic bed monitoring (such as congenital heart disease, abdominal wall defects, or congenital diaphragmatic hernia), inherited metabolic disorders, hydrops fetalis, TORCH infections, multiple organ failure, spontaneous intestinal perforation, lesions in the area where the NIRS sensor was placed, or

whose UVC was removed for any reason before 24 hours, as well as those with severe anemia or polycythemia, were excluded from the study. Infants with a birth hemoglobin (Hb) level of 10 g/dl or below were considered severely anemic, and those with a Hb level of 22 g/dl or above were considered polycythemic.

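### The catheter-in-place comparison limits days for UVC (+) infants only, so postnatal age or depletion can bias it, depending on how the days are combined

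*Combined protocol and SAP*

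**What the plan says.** Section 2.5(b) records splanchnic saturation and oxygen extraction continuously. The values "were calculated as means on each day of the first week of life (WOL"). Three kinds of comparison follow.

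- **Whole week:** "Continuous measurements taken during the first WOL were compared both between the groups and within each group on a day-to-day basis".
- **Within UVC (+) infants:** before and after placement, and before and after removal.
- **Additional, between groups:** "the daily means in the UVC (+) Group during the period when the UVC was in place were compared with the daily means in" controls. Only the UVC (+) side is limited. No index removal day is given for controls, and the day-to-day wording of the whole-week comparison is not repeated.

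On follow-up, "monitoring was carried out for 1 week using NIRS", but "Splanchnic NIRS monitoring was terminated 24 hours after the removal of the UVC". No other stopping point is given for controls.

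On matching, section 1.2 says "Infants who did not have a UVC but matched the Study Group regarding gestational age and birth weight constituted the UVC (-) Control Group". It does not say whether this was done infant by infant or at group level. The same section excludes infants "whose UVC was removed for any reason before 24 hours".

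Section 1.4 gives a recommended maximum catheter duration of 7-10 days, but no removal criteria and no distribution of removal days. Section 1.5.2 lists independent two-group tests, a repeated-measures ANOVA and a covariance analysis. It names no covariates and gives no rule for days after removal.

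**The concern.** The restriction is one-sided, and the two ways of carrying out the comparison fail differently.

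- **One average per infant.** A UVC (+) infant's mean covers the days up to removal, while a control's mean covers the whole week. The groups then differ in postnatal age by construction. Section 1.3 raises enteral volume daily, so splanchnic conditions may well change with age in both groups.
- **Day by day.** Age is aligned. From the first removal on, however, the UVC (+) side holds only infants still catheterised, while every control remains. If removal is related to the infant's condition, those left no longer represent the group to which the controls were matched.

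This is the only between-group comparison confined to time with the catheter in place, and determining the effect of the catheter is among the stated primary outcomes. As written, it could show a difference, or hide one, with no catheter effect.

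**Working it through.** **Inputs from the documents.** One week of daily means (section 2.5); at least 21 infants per group and a planning effect size of 0.8 (section 1.5.1). The plan gives no figure for this bias. The 21 is used here only as the group size. It reproduces with a one-sided 5% t-test (20.03, rounded up) but not with a two-sided one (25.5, so 26). The plan does not state sidedness; that is a separate matter.

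**Assumed inputs; the documents give none of these.** Catheter in from day 1; last catheter day spread evenly over days 2-7, or over days 5-7, or day 7 for all; the same linear age drift in both groups; SD of an observed daily mean = 1; within-infant correlation 0.6; correlation 0.5 between an infant's stable underlying level and removal day; no true catheter effect.

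**Step 1: averaging per infant.** With last catheter day r, an infant's mean catheter-in day is (1 + r)/2. The control mean day is (1 + 7)/2 = 4. Bias = drift × gap in mean day.

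| Last catheter day | Mean catheter-in day | Gap | Bias at 0.1 SD/day | Bias at 0.2 SD/day |
|---|---|---|---|---|
| Days 2-7 | (1.5+2+2.5+3+3.5+4)/6 = 2.75 | 1.25 | 0.125 SD | 0.25 SD |
| Days 5-7 | (3+3.5+4)/3 = 3.5 | 0.5 | 0.05 SD | 0.10 SD |
| All day 7 | 4 | 0 | 0 | 0 |

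**Step 2: day by day.** The drift is equal on both sides on any given day, so the age bias is 0. For depletion, let p be the share still catheterised. The mean of the top fraction p of a standard normal is φ(z)/p, with z its cut-off. Bias in observed SD = 0.5 × √0.6 × φ(z)/p, where √0.6 = 0.775 converts from SDs of underlying level to SDs of observed daily means.

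| Removal spread | Day | p | Infants of 21 | φ(z)/p | Bias |
|---|---|---|---|---|---|
| Days 2-7 | 3 | 5/6 | 17.5 | 0.300 | 0.12 SD |
| Days 2-7 | 5 | 1/2 | 10.5 | 0.798 | 0.31 SD |
| Days 2-7 | 7 | 1/6 | 3.5 | 1.499 | 0.58 SD |
| Days 5-7 | 7 | 1/3 | 7 | 1.091 | 0.42 SD |

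**Step 3: null simulation.** With 21 per group, 1,500 simulated studies per scenario and a two-sided 5% t-test, the results agree.

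- Per-infant averaging, removal over days 2-7: difference about 0.13 SD at 0.1 SD/day and 0.25 SD at 0.2 SD/day. False-positive rates are 0.07-0.08 and 0.16-0.18.
- Per-infant averaging, removal on days 5-7: 0.05 and 0.10 SD, with false-positive rates of 0.045 and 0.055.
- Same-day contrasts at correlation 0.5: 0.12 SD on day 3, rising to about 0.58 SD on day 7 (about 0.4 SD with removal on days 5-7).

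**Step 4: the remedy under the same null.** When each control is cut to a UVC (+) infant's window and one mean per infant is compared, the difference is -0.01 to 0.01 SD. The false-positive rate is about 0.04-0.07, for drifts of 0 to 0.3 SD/day and selection correlations of 0 to 0.8.

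**The case against.** Several points on the other side stand.

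- **Day by day is the more natural reading.** The parameters are daily means, and the whole-week comparison is explicitly day to day. Under that reading there is no age bias. A reader might infer that postnatal age confounds the comparison in any case; the text does not support that. It leaves the alignment open, which is why both readings need an answer.
- **Removal is not said to follow recovery.** A reader might infer that recovering infants lose the catheter first. No section says so. Removal for malposition or a complication could weaken the selection or reverse it.
- **Truncation may be small.** A 7-10 day recommended maximum allows most catheters to stay in through the week, and then the bias approaches zero. Against this, if the 24 hours of recording after removal are to fall within one week of monitoring, removal must come by about day 6. The documents do not settle which applied.
- **The comparison is additional.** The whole-week and the before/after comparisons are named among the primary outcomes, and the within-infant ones do not depend on control days. The whole-week comparison is no refuge, though: UVC (+) recording stops 24 hours after removal, so it is truncated in a similar way.
- **Covariance analysis is planned.** It names no covariates and does not mention postnatal day or catheter status, so it cannot be counted as a safeguard.
- **Individual pairs are not documented.** The matching sentence and the independent-samples tests are compatible with group-level matching, so a remedy that needs pairs may not be applicable.

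**Conclusion.** The concern holds in limited form. The one-sided restriction is in the text, and no other section repairs it. Averaging per infant confounds group with postnatal age; comparing day by day removes that but exposes later days to depletion of the UVC (+) side.

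The sizes are conditional on assumptions. The age bias is 0.125 to 0.25 SD for drifts of 0.1 to 0.2 SD/day with removal over days 2-7, 0.05 to 0.10 SD with removal on days 5-7, and zero if all catheters stay in for 7 days. The day-7 depletion bias at correlation 0.5 is about 0.4 to 0.6 observed SD. At the upper end it rests on only 3-4 of 21 infants. It is zero if removal is unrelated to the infant's level, and its direction is unknown.

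A reader might set a day-7 figure of 0.75 (0.5 × 1.499) against the planned effect size of 0.8. That figure is in SDs of underlying level; the observed-scale equivalent here is 0.58, so the two should not be compared directly. Nor do the documents show that any bias occurred: they give no removal days, reasons or drift.

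**What to change.** - State how days are combined in this comparison.
- Assign each control the placement and removal days of its matched UVC (+) infant. If matching was at group level, draw an index window from the UVC (+) distribution within gestational-age and birth-weight strata.
- Compute one mean per infant over those same postnatal days and compare these means, so that every UVC (+) infant contributes once.
- Treat any day-by-day contrast as descriptive. Report the number still catheterised on each day, and the removal days and reasons. Cutting control days alone does not remove selection from same-day contrasts.

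The cost is re-analysis: placement and removal times and daily means are already recorded, though removal reasons may have to be retrieved. Group-level matching adds the work of drawing index windows. The price is fewer control infant-days and slightly wider intervals. The simulation tested selection on a stable infant level only, so removal that responds to an infant's changing course could leave some residual bias.
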